
6. PARTICIPANT IDENTIFICATION

Study participants are defined as healthy participants aged between 18 and 60 years old and willing to participate in the study. This study will take place at the Shoklo Malaria Research Unit (SMRU) research centre in Mae Sot.

6.1. Inclusion criteria

- Healthy male or female participant judged by a responsible physician with no abnormality identified on a medical evaluation;
- Thai, Burmese or Karen ethnicity;
- Aged \geq 18 to <60 years old;
- Living in Mae Sot city for the last 12 months;
- Willing to participate in the activity and able to give informed consent for participating in the study;
- Able to tolerate direct mosquito exposure.

6.2. Exclusion criteria

- History of travel in a malaria endemic are (rural village) in the last 12 months, or plan to do so during the study;
- Medication or condition deemed to interfere with the outcome measure by a responsible physician;
- Moderate and severe anemia (haemoglobin concentration less than 110 g/L of blood);
- Hypersensitivity or anaphylaxis to mosquito bites;
- Pregnant women;
- Breastfeeding women.

7. STUDY PROCEDURES

7.1. Recruitment and informed consent of study participants

The study will be spread through word of mouth in Mae Sot by the study team and then interested participants will contact SMRU. The persons interested in participating in the study will be invited to individual and group discussions with the study team during which more details of the study will be presented and potential participants will be given the opportunity to ask questions. The persons willing to take part in the study will be appointed for the screening visit. Participants' presenting to the screening visit must personally and voluntarily sign and date the latest approved version of the informed consent form before any study specific procedures are performed. The Participant Information and Informed Consent Form will be presented to the participants detailing no less than: the exact nature of the study; what it will involve for the participant; the implications and constraints of the protocol and any risks and benefits involved in taking part. It will be clearly stated that the participant is free to withdraw from the study at any time for any reason without prejudice to future care, and with no obligation to give the reason for withdrawal. The participant will be allowed as much time as they wish to consider the information, and the opportunity to question the Investigator or other independent parties to decide whether they will participate in the study. The informed consent and procedures visit will take approximatively one hour.

Written Informed Consent will be obtained by asking the participant to sign and date the informed consent form. If the participant is illiterate, they will be asked to give a thumb print, leaving the date field blank and a literate impartial witness will be asked to sign and date the consent form, confirming that the participant understands what they are being asked to do and have given consent. The form will also be signed and dated by the person who presented and obtained the Informed Consent. The person who obtained the consent must be suitably qualified and experienced, and authorised to do so by the Principal Investigator. A copy of the signed Informed Consent will be given to the participant. The original signed form will be retained at the study site.

7.2. Screening visit

Subjects will be screened to assess eligibility (visit 1). Informed consent will be obtained before any screening procedures are conducted. The following screening procedures will be carried out no longer than 30 days before the first baseline visit:

- Personal data collection including name, age, date of birth, sex, ethnicity, address and telephone number;
- A comprehensive physical examination including measurement of height, body weight and vital signs (blood pressure, respiratory rate, body temperature and heart rate) and medical history assessment including travel history outside Maesot town during the past 3 months;
- A pregnancy test if indicated (cost of the test will be covered by the study);
- Venous blood collection (2 mL) in order to perform complete blood count and measure haemoglobin concentration.

Participants will also be informed about the importance of avoiding being bitten by mosquitoes independently of the study challenges during the follow-up. They will be provided with insecticide-impregnated mosquito bed-nets and skin repellent (N,N-diethyl-meta-toluamide 20%). Participants who will be allocated to the *Aedes* groups will receive counselling about larval source management in order to limit exposure to mosquito bites that may happen independently of the study challenges. Sand Abate granules (temephos 1%) will be provided free of charge to participants who need it.

Data collected during the screening and subsequent visits will be recorded in the Case Report Form (CRF) and stored in the study database. The CRF will be pseudonymized using the participant identification code, date of enrolment, initials, sex and date of birth. Personal data (name, telephone number and address) will be recorded and stored separately, allowing linkage of study data with participant's details by the study team.

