7.3. Baseline visits

One hundred and fifty healthy subjects who fulfil the eligibility criteria will be recruited to the study. Baseline visits will be scheduled at day 0 and day 7 (visit 2 and 3). Baseline visits will include capillary blood and venous blood collection (Appendix C). Randomization will be performed during visit 2.

For baseline and subsequent visits, in case participant fails to come on the exact day a visit is scheduled, he/she will be allowed to come for a retake any other working day of the study team until the next scheduled visit.

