7.5. Subsequent visits

From day 14 to day 56, participant will be exposed to bites of laboratory-adapted colonies of Anopheles minimus, An. maculatus and An. dirus, Aedes aegypti or Ae. albopictus reared at the SMRU. Appropriate quality control measures will be implemented such as to guarantee the absence of human pathogen in the mosquito batches used in this study and withdraw any participant with hypersensitivity to mosquito bites (see section 13.5.1. Risk of mosquito exposure). Participants will receive a total of either 35 or 305 mosquito bites per participant in 7 challenges split over 6 weeks (see mosquito intervention section). Each visit will include physical examination, vital signs assessment, mosquito exposure, capillary blood and venous blood collection according to Appendix C. Immediate skin reactions (20-30 min after mosquito bites) will be recorded after each mosquito feeding assay. Delayed skin reactions (24-36 hours after mosquito bites) will be recorded after the day 14, 21 challenges, requiring additional visits at day 15, 22. After day 56, each visit will include capillary blood and venous blood collection according to Appendix C. The study procedure will take approximatively 1 hours for medical history assessment, physical examination and vital sign assessment, 15 minutes for blood sampling and 30-90 minutes for the challenge with mosquito bites (depending on the number of repeats needed to reach the target number of mosquito bites). During the exposure visits, the participants will be kept in observation for an additional hour after the challenge before being allowed to leave the study site. Participants will be requested not to apply any lotions, ointments, creams, powders, perfumes, antiperspirants, repellents, or attractants prior to each exposure visit. Participants will be provided palliative antipruritic medication consisting in 1% diphenhydramine hydrochloride cream and oral cetirizine at the dose of 10 mg per day in order to relieve itching from mosquito bites (103, 104). In addition, participants will be provided with a mosquito bed net and skin repellent in order to minimize uncontrolled natural exposure to mosquito bites that can happen independently of the study challenges.

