7.9. Discontinuation/Withdrawal of Participants from Study

Each participant has the right to withdraw from the study at any time.

In addition, the Investigator may discontinue a participant from the study at any time if the Investigator considers it necessary for any reason including:

- Ineligibility (either arising during the study or retrospectively having been overlooked at screening)
- Significant protocol deviation
- Significant non-compliance with study requirements
- Loss to follow up
- Hypersensitivity to mosquito bites or anaphylaxis

The data collected until the point of withdrawal will be included in the study and this is stated in the participant information sheet unless participant refuse to do so. The participant will be replaced with another person and the replacement will be assigned to the same study arm.

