8. MOSQUITO INTERVENTION

From day 14 to day 56, participant will be exposed to bites of laboratory-adapted colonies of *An. minimus, An. maculatus* and *An. dirus, Ae. aegypti* or *Ae. albopictus* reared at the SMRU. Appropriate quality control measures will be implemented such as to guarantee the absence of human pathogen in the mosquito batches used in this study and withdraw any participant with hypersensitivity to mosquito bites (see section 13.5.1. Risk of mosquito exposure). In the low-exposure groups, participants will be exposed to 5 mosquito bites at weekly intervals from day 14 to day 56 (seven challenges with 5 mosquito bites/challenge over six weeks, yielding a total of 35 mosquito bites). In the high-exposure group,

participants will be exposed to 5 mosquito bites on day 14 and then to 50 mosquito bites at weekly intervals from day 21 to day 56 (one challenge with 5 mosquito bites and six challenges with 50 mosquito bites/challenge over 6 weeks, yielding a total of 305 mosquito bites).

For the low-dose challenge, five 5 to 7-day-old nulliparous female imagoes (i.e. that have never blood fed before) will be introduced individual into 50 mL plastic tube covered with netting material. For high-dose challenge, 47 mosquitoes will be split into four plastic cups of 10 cm in diameter covered with netting material (three cups with 12 mosquitoes and one cup with 11 mosquitoes), and 3 mosquitoes will be introduced individually into 50 mL plastic tubes. At first, three mosquito bites from individual 50 mL tubes will be administered on participant's arm. Then, the remaining mosquito containers will be placed on participant's left arm, calf, thigh or back skin, and the lights will be dimmed to encourage mosquito bites administered on participant's arm will be used to assess immediate and delayed skin reactions as described previously (37). Immediate and delayed skin reactions will be recorded respectively 20-30 min and 24-36 hours after the day 14 and day 21 challenges, requiring additional visits at day 15 and 22.

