Mosquitoes will be given the opportunity to feed on participant's skin for 30 min. The number of bites actually received by participants will be assessed by counting the number of engorged mosquitoes at the end of the 30-minute exposure time. If not all mosquitoes would have successfully engorged, participant will be exposed to additional mosquitoes using the same procedure in order to reach the target number of bites (participant may be exposed to mosquito bites up to three times at each visit). Partially engorged mosquitoes will not be discarded and we be counted as fully engorged specimens. In case the challenge will be carried out in the morning, mosquitoes will be starved overnight. In case the challenge will be carried out in the afternoon, mosquitoes will be staved since 9 am. Mosquitoes used to challenge each study participant will be immediately killed at the end of the challenge using 70% ethanol. The mosquito exposure will be performed by study staff under supervision of a medical doctor. The challenge with mosquito bites will take 30 minutes and may be repeated twice in case not all mosquito engorge during the first challenge. The participants will be kept in observation for an additional hour before being allowed to leave the study site. During that time, participants will be provided with a snack and refreshment.

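### Pregnancy is an exclusion, but the only named check is one conditional test at screening, up to 44 days before the first bites and 86 before the last; test again at visit 4

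*Protocol*

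**What the plan says.** Protocol 6.2 lists "Pregnant women" among the exclusions, and SAP 3.2 also excludes pregnancy. The one check named is in protocol 7.2, at visit 1: "A pregnancy test if indicated (cost of the test will be covered by the study"). What would indicate a test is not stated.

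The later visits are described without a pregnancy check:

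- Protocol 7.3, visits 2 and 3: "Baseline visits will include capillary blood and venous blood collection (Appendix C). Randomization will be performed during visit 2".
- Protocol 7.5, exposure visits: "Each visit will include physical examination, vital signs assessment, mosquito exposure, capillary blood and venous blood collection according to Appendix C". Its estimate of visit length also mentions a medical history assessment, but Appendix C marks medical history as not done at any visit after the first.
- Protocol section 8, high-dose arms: "exposed to 5 mosquito bites on day 14 and then to 50 mosquito bites at weekly intervals from day 21 to day 56". Low-dose participants receive five bites on the same days.

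The discontinuation section (protocol 7.9) lets the investigator withdraw a participant for reasons that include "Ineligibility (either arising during the study or retrospectively having been overlooked at screening"). It adds: "The participant will be replaced with another person and the replacement will be assigned to the same study arm".

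The two documents give different screening windows. Protocol 7.2 allows up to 30 days before the first baseline visit, and Appendix C and SAP Table 2 agree. The text of SAP 3.2 gives day -14 to day -1.

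**The concern.** Pregnancy status can change between screening and the end of exposure, and the discontinuation section foresees eligibility being lost during the study. For pregnancy, however, no listed procedure would bring such a change to light. As written, a woman who becomes pregnant after visit 1, or who was not tested there because a test was not thought indicated, could go on being challenged unless she says so or someone notices.

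What is at stake is whether the sponsor's own exclusion is applied to healthy volunteers during the weeks when they are bitten. It is a participant-safety and eligibility matter. Sample size, power and type I error are not affected.

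**Working it through.** **Inputs.** Maximum screening lead: 30 days (protocol 7.2), or 14 days (SAP 3.2). Challenge days: 14, 21, 28, 35, 42, 49 and 56, which are visits 4, 6 and 8 to 12 (protocol section 8, Appendix C).

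**The plan's own figure.** Protocol 13.5.1 gives 112 to 142 days from visit 1 to visit 20. The upper end is 30 + 112 = 142, which matches. The 30 days therefore count back from day 0.

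**Age of the check at each challenge** = screening lead + challenge day. With a test at visit 4, age = challenge day − 14.

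| Challenge day | Protocol 7.2 window (30 + day) | SAP 3.2 window (14 + day) | With a visit 4 test (day − 14) |
|---|---|---|---|
| 14 | 44 | 28 | 0 |
| 21 | 51 | 35 | 7 |
| 28 | 58 | 42 | 14 |
| 35 | 65 | 49 | 21 |
| 42 | 72 | 56 | 28 |
| 49 | 79 | 63 | 35 |
| 56 | 86 | 70 | 42 |

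The second and third columns are maxima for scheduled days. Missed visits may be retaken (protocol 7.3). If that is read as up to 6 days late, before the next weekly visit, the first and last ages become 50 and 92 days under the 30-day window, and 34 and 76 under the 14-day window.

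**Other routes by which a pregnancy might be recognised:**

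- a case report form and adverse event form at each visit (protocol 9.3);
- physical examination at visits 4 to 12 (Appendix C);
- medical supervision of the challenges: "The mosquito exposure will be performed by study staff under supervision of a medical doctor" (section 8);
- safety board review after days 15 and 22 (9.4);
- a medical history at subsequent visits, if the time estimate in 7.5 is right and Appendix C is wrong.

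None of these names pregnancy. It is not among the pre-specified adverse events in 9.3 or the excluding reactions in 9.4. Each route depends on the participant volunteering the information or on chance recognition, except perhaps the medical history, where the documents conflict on whether it is taken at all.

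**Not calculable.** The documents give neither the number of women to be enrolled nor a pregnancy rate, so no expected count is offered.

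**The case against.** The strongest reply has four parts.

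1. *The exclusion is an entry criterion.* SAP 3.2 ties the criteria to randomisation and has them checked at screening, and withdrawal under the discontinuation section is at the investigator's discretion. This stands: a reader might infer that the protocol breaks its own rule, but it nowhere requires repeated verification. The weaker point survives, that a ground for withdrawal was foreseen and, for pregnancy, nothing listed would trigger it.

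2. *The risk is very small.* Protocol 13.5.1 describes females that have never fed on blood, colonies maintained on screened donor blood, and *Aedes* colonies screened for dengue, Zika and chikungunya. This also stands. A reader might infer that pregnant participants face a real infection hazard. The documents do not support that, and they give no reason for the exclusion.

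3. *It may already be covered.* A medical history at exposure visits would be the natural place to ask, and consent pages and case report forms are not in our copy. This stands in part. Protocol 7.5 and Appendix C disagree about the history, and the unseen material cannot be judged. If a prompt exists there, adding it to 7.5 costs almost nothing.

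4. *The weekly question is itself self-report.* Correct. One might be tempted to say that asking each week shortens the gap between checks to seven days, but a question is not a test. Unless an answer prompts a test, the last test is still 42 days old at the final challenge. Only the visit 4 test is a new objective check.

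A reader might also count the bites given after the last safety board review as a measure of the problem. That does not work, because 9.4 sets the board up to review adverse events and bite reactions, not pregnancy.

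**Conclusion.** The point holds as a cheap safety improvement. The only named pregnancy check can be up to 44 days old at the first challenge and 86 at the last under protocol 7.2, or 28 and 70 under SAP 3.2, and its condition is undefined. No later visit names a check.

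The figures assume visits on scheduled days and screening at the earliest permitted date; most women would be screened nearer to day 0 if recruitment moves quickly. The conclusion does not depend on which window applies. It claims no specific harm, no breach of the protocol and no effect on the analysis. It rests on the protocol and SAP text alone, without the consent pages or case report forms. Some SAP passages (7.1, 8.3) are in the past tense, so follow-up may be complete. In that case the change matters for any remaining participants or for reuse of this challenge model.

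**What to change.** In protocol 7.5 and Appendix C:

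- At visit 4, before the first bites, give a pregnancy test to every woman who could be pregnant, in place of the undefined condition in 7.2.
- At visits 6 and 8 to 12, ask about and record pregnancy status during the examination already scheduled, and test if pregnancy is possible (for example, after a late period). This supplements the visit 4 test and does not replace it.
- If a test is positive, stop the challenges, then discontinue and replace the participant under the discontinuation section.
- Settle whether a medical history is taken after visit 1, so that 7.5 and Appendix C agree.

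The cost is one test kit per eligible woman at visit 4, one question at six existing visits, and an occasional further test. No visits are added, and the study already pays for the test at screening.

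There is one statistical side effect. A woman found pregnant at visit 4 has already been randomised and will normally have given baseline samples, so under SAP 7.2.1 she stays in the intention-to-treat set without having been exposed. Also testing at visit 2, before the envelope is opened, would make this less frequent, though it would not catch a pregnancy arising between day 0 and day 14. The SAP needs no change, since its section 1.2 refers readers to the protocol for clinical assessments.

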7.4. Randomization

A block randomization schedule will be generated using the block.random() function of the R package *psych* version 1.8.12 using variables species (*An. minimus, An. maculatus, An. dirus, Ae. aegypti* and *Ae. albopictus*) and dose (35 or 305 bites in total) yielding a list of 15 blocks with 10 participants each (total of 150 participants). Following screening and eligibility assessment, participant will be assigned a study arm during visit 2 through the randomization schedule. Individual, sealed and sequentially numbered envelopes will be provided for the study site with one envelope per participant, indicating the allocation.

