5.1 Randomisation and Blinding

A block randomization schedule will be generated using the block.random function of the R package psych version 1.8.12 (28) with variables species (*An. minimus, An. maculatus, An. dirus, Ae. aegypti* and *Ae. albopictus*) and dose (35 or 305 bites in total), yielding an ordered list of 15 blocks with 10 participants per block randomly assigned to one of the 10 study arms.

An allocation sequence will be implemented using individual, sealed and sequentially numbered envelopes. Following screening and eligibility assessment, participants will be assigned to a study arm during visit 2 using the randomization schedule.

An allocation sequence will be generated by a study investigator. At the beginning of the study, the study coordinator will prepare a set of case report forms (CRFs) with preprinted subject identification codes and attach the sealed envelope containing intervention allocation to the CRF. Study nurses will then assign a subject identification code to participants by chronological order of enrollment in the study and the envelope will be opened during visit 2.

Allocation of intervention will be masked to outcome assessors (laboratory personnel who will process the serum samples) and data analysts. In order to do so, allocation of intervention in study datasets that contain this information will be masked until the results of the final analysis are made available to study investigators.

Amendment to SAP 23/03/2023

In order to fit additional models assessing the effects of concordant vs discordant species of exposure on antibody analyses (detailed in Section 9.2), after consultation with Principal and Study Investigators, the antibody data were locked and the biostatisticians were un-blinded.

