Due to differences (in terms of time) between individuals transitioning from baseline, to exposure and post-exposure periods, linear splines representing these periods of fixed time were unable to be estimated. Instead, the overall effect of time will be estimated (independent of any exposure and thus representing the baseline period), with the exposure and post-exposure periods fitted as a categorical time-varying variable. To estimate the extent to which antibody levels associated with biting are dependent on time, interaction terms for the intervention periods by time will be estimated.

The change in antibody levels (as a continuous outcome and binary response) over time, and in response to *Anopheles* biting exposure, will be analysed using generalised estimating equations (GEEs). The specification of an autoregressive correlation structure will better account for high-levels of serial correlation in antibody levels within individuals over time. Furthermore, a marginal model will allow for robust inference of the estimated effects of the exposure and post-exposure periods on antibody levels.

9.2 Moderating effect of mosquito biting species or dose of exposure on antibody level and seropositivity

To investigate if changes in antibody levels over time vary according to mosquito species or biting dose, interaction terms will be fitted between time, exposure species (*An. minimus, An. maculatus, An. dirus, Ae. aegypti* and *Ae. albopictus*) and biting dose (35 or 305 bites), respectively.

Amendment to SAP 23/03/2023

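### Larval-source counselling is tied to the Aedes groups and placed before allocation, so background Aedes biting may differ by arm and the low-dose species contrast on Aedes peptides may be attenuated

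*Protocol*

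**What the plan says.** Protocol 7.2 (Screening visit) sets out two layers of protection against natural bites. The first is for everyone: "They will be provided with insecticide-impregnated mosquito bed-nets and skin repellent". Protocol 7.5 repeats this for follow-up. The second is tied to species: participants who will be in the Aedes "groups will receive counselling about larval source management in order to limit exposure to mosquito bites" unrelated to the challenges. Temephos granules "will be provided free of charge to participants who need it", with no arm named.

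Screening is visit 1, up to 30 days before day 0. Protocol 7.3 states "Randomization will be performed during visit 2", Protocol 7.4 that each "participant will be assigned a study arm during visit 2 through the randomization schedule", and SAP 5.1 that "the envelope will be opened during visit 2".

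SAP 2.2 lists antibodies to aegN-term34kDa and albN-term34kDa among the primary endpoints. For species differences, SAP 9.2 says "interaction terms will be fitted between time, exposure species" and biting dose. The concordant/discordant models added in March 2023 are listed for anti-SG6-P1 antibodies only.

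SAP 3.1 describes Mae Sot as free of Anopheles and makes no such statement about Aedes. Its account of the intervention mentions advice to avoid Anopheles bites and a travel history at each visit. It does not mention larval-source counselling, temephos, or any record of natural Aedes biting.

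**The concern.** The counselling is a co-intervention meant to change the very exposure that the biomarker is supposed to measure, and it follows randomised species. No arm goes without challenge, so for an Aedes peptide the three Anopheles species (90 participants) are the only concurrent Aedes-unchallenged comparators. If counselling lowers natural Aedes biting in the Aedes arms alone, the between-species contrast estimates challenge bites minus averted natural bites, not challenge bites alone. A useful Aedes biomarker could then look less sensitive than it is, most of all at 35 bites. Because neither natural Aedes biting nor uptake of the advice is described as recorded, the analysis could not separate the two afterwards.

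The placement is a second problem. Staff cannot know at visit 1 who will be in an Aedes group while the envelopes are sealed. The text leaves open when the counselling is given and to whom.

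**Working it through.** **Design figures, reproduced from the protocol.** Low dose: 7 × 5 = 35 bites. High dose: 5 + 6 × 50 = 305 bites. Participants: 15 blocks × 10 = 150, of whom 2 species × 2 doses × 15 = 60 are in Aedes arms and 3 × 2 × 15 = 90 in Anopheles arms.

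**Inputs that the documents do not give (assumptions).** Natural Aedes bites per week, b; proportional reduction due to counselling, r. The window is seven weeks, from the first challenge (day 14) to the first post-exposure sample (day 63).

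**Averted bites = b × r × 7, compared with the challenge total:**

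- b = 2, r = 25%: 3.5 bites; 3.5/35 = 10%; 3.5/305 = 1.1%.
- b = 5, r = 30%: 10.5 bites; 10.5/35 = 30%; 10.5/305 = 3.4%.
- b = 10, r = 50%: 35 bites; 35/35 = 100%; 35/305 = 11.5%.
- b = 20, r = 50%: 70 bites; 70/35 = 200%; 70/305 = 23.0%.

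At 100% the low-dose contrast in bites is cancelled. Above that it changes sign.

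**Does the direction survive on the antibody scale?** A simple kinetic model was used. Each bite adds one unit and levels decay with half-life h. Natural bites arrive daily, and participants start at steady state. Baseline is the mean of days 0 and 7. Mid-case: b = 5, r = 30%, h = 28 days, counselling from day 0 (visit 2).

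- Background level: (5/7) × q/(1 − q) with q = 2^(−1/28), giving 28.50 units.
- Low-dose challenge contribution at day 63: 5 × Σ 2^(−k/4), k = 1 to 7, = 18.57 units.
- Contrast with no counselling: log2[(28.50 + 18.57)/28.50] = 0.72.
- Background at day 63 with counselling: 28.50 × (0.7 + 0.3 × 2^(−63/28)) = 21.75. Level contrast: log2[(21.75 + 18.57)/28.50] = 0.50.
- Baseline with counselling: mean of 28.50 and 28.50 × (0.7 + 0.3 × 2^(−7/28)) = 27.82. Change-from-baseline contrast: log2(40.32/27.82) = 0.54.

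With b = 20 and the rest unchanged, the low-dose contrast goes from 0.22 to −0.11 (level) or −0.08 (change). Across b = 1, 5, 20, r = 10%, 30%, 50% and h = 14, 28, 84 days, with counselling from visit 2, the low-dose contrast falls or reverses in all 27 combinations on both measures.

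**High dose, mid-case.** 2.82 becomes 2.77 (level) or 2.80 (change). Over the same grid the level contrast falls in all 27 combinations, but the change-from-baseline contrast falls in only 15.

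**High versus low within the Aedes arms.** Both doses receive the counselling. The difference is 153.75 units with or without it; on log2 it rises from 2.09 to 2.27. No attenuation.

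**After the fix.** With counselling in all arms, the mid-case low-dose difference is again 18.57 units. The log2 contrast is 0.89, above 0.72, because background falls equally in both arms.

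**The case against.** The strongest reply has four parts.

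First, the sentence may simply be misplaced. It looks ahead to allocation and names no visit for delivery. That is fair. A reader might infer that Aedes participants were identified and counselled before allocation. The documents do not support this: counselling confined to the Aedes arms and counselling before arms are known cannot both hold while the envelopes are sealed. What stands is an instruction that cannot be followed where it is placed.

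Second, the direction is conditional. If counselling were already acting 30 days before day 0, the mid-case low-dose change from baseline would go from 0.72 to 0.73, and with a 14-day half-life from 0.83 to 0.97, away from the null. This is correct arithmetic, but that timing requires knowing the arm before visit 2. With delivery at visit 2, attenuation at low dose is consistent. A blanket statement of bias toward the null is not justified.

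Third, the affected analysis is narrow. No contrast using Anopheles arms as comparators is written out for the Nterm-34kDa peptides; they are reached only through the general species interaction. In the SG6-P1 concordance contrasts the Aedes arms are the comparators, and natural Anopheles exposure in Mae Sot is said to be absent. Seropositivity thresholds come from external sera. All of this stands and limits the reach of the point.

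Fourth, everyone already receives avoidance advice, nets and repellent, temephos is not restricted by arm, and limiting outside bites in the Aedes arms helps their within-person kinetics. These reduce the likely effect. They do not explain why the advice should differ by arm, since giving it to everyone keeps the benefit.

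**Conclusion.** The plan has a co-intervention that differs by randomised species and acts on the exposure being measured, with timing that conflicts with allocation at visit 2. Both are plain from the text. That background Aedes biting differs between arms is a risk, not a fact: the documents give no biting rate, no effect of counselling and no uptake, and the SAP does not show whether the counselling was given.

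If it starts at visit 2 and works, the Aedes-versus-Anopheles contrast on the two Nterm-34kDa peptides is attenuated. Under the assumed 2 to 20 bites a week and 25% to 50% reduction, the averted bites are 10% to 200% of the 35-bite challenge and about 1% to 23% of the 305-bite challenge. The point therefore matters mainly for the low-dose Aedes arms and is small at high dose unless natural biting is heavy. A reader might infer that all Aedes biomarker results are biased toward the null; dose contrasts within the Aedes arms and the SG6-P1 concordance contrasts are not attenuated by this. In an exploratory study, this is an inexpensive improvement worth making, not a flaw that undermines the trial.

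**What to change.** In Protocol 7.2, give the same larval-source counselling to all 150 participants at screening, regardless of arm, and bring the intervention text in SAP 3.1 into line. This removes the difference between arms and the timing conflict together. Temephos is already offered to anyone who needs it. The cost is a few minutes of counselling for 90 more participants and possibly some extra granules, with no new visit.

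SAP 7.1 describes data review after the last day-112 visit in the past tense, so conduct may be complete. In that case, state at which visit and to which arms the counselling was given, report counselling and temephos use by arm where recorded, and note the possible attenuation when interpreting low-dose Aedes-antigen contrasts between species. This costs a short table and a sentence or two in the report.
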